4.6.2. Secondary and Other Endpoints

The secondary and other endpoints listed below will evaluate the effect of IV FCM relative to placebo. These will be analysed on the FAS and as a sensitivity analysis on the PP set, using adjudicated events based on the final decision of the CEC.

Secondary endpoints:

- The composite of recurrent CV hospitalisations and CV death up to 52 weeks after randomisation.
- HF hospitalisations up to 52 weeks after randomisation (analysed as a recurrent event).
- CV mortality analysed as time to first event up to 52 weeks after randomisation.
- The composite of HF hospitalisations or CV death analysed as time to first event up to 52 weeks after randomisation.
- Days lost due to HF hospitalisations or CV death up to 52 weeks after randomisation.

Hochberg's procedure will be used to control the overall Type I error for the evaluation of the secondary endpoints on FAS at the FWER of 5% two-sided. All secondary endpoints will be analysed as described further in this section, p-values will be sorted from the smallest to the largest and compared with Hochberg's critical values (see Table 5). The highest p-value with lower value than the Hochberg's critical value will be chosen. This p-value and all lower p-values will be considered statistically significant at overall level 5% two-sided.

Table 5 Hochberg's Critical Values

Ordered p-values	Hochberg's critical values
p-value ₁	0.05/5 = 0.01
p-value ₂	0.05/4 = 0.0125
p-value ₃	0.05/3 = 0.0166
p-value ₄	0.05/2 = 0.025
p-value ₅	0.05/1 = 0.05

Other endpoints:

- The composite of recurrent HF hospitalisations and CV death up to 30 days after randomisation.
- The composite of recurrent CV hospitalisations and CV death up to 30 days after randomisation.
- The composite of HF hospitalisations or CV death analysed as time to first event up to 30 days after randomisation.
- The composite of CV hospitalisations or CV death analysed as time to first event up to 30 days after randomisation.
- HF hospitalisations up to 30 days after randomisation (analysed as a recurrent event).
- HF hospitalisations up to 30 days after randomisation (analysed as time to first event).
- HF hospitalisations up to 52 weeks after randomisation (analysed as time to first event).
- CV hospitalisations up to 30 days after randomisation (analysed as a recurrent event and time to first event).
- CV hospitalisations up to 52 weeks after randomisation (analysed as a recurrent event and time to first event).
- The composite of CV hospitalisations or CV death analysed as time to first event up to 52 weeks after randomisation.
- CV mortality analysed as time to first event up to 30 days after randomisation.
- All-cause mortality analysed as time to first event up to 30 days after randomisation.
- All-cause mortality analysed as time to first event up to 52 weeks after randomisation.
- Proportion of subjects with an event (HF hospitalisations, CV hospitalisations, CV mortality; composite and individual categories).
- Change from baseline in NYHA functional class as assessed at 6, 12, 24, and 52 weeks after randomisation.
- Change from baseline in the Kansas City Cardiomyopathy Questionnaire-12 (KCCQ-12) up to 52 weeks after randomisation. *Note: Described in section 4.8.10.*
- Change from baseline in the European Quality of Life – 5 Dimensions questionnaire up to 52 weeks after randomisation. *Note: Described in section 4.8.10.*
- Days lost due to HF hospitalisations or CV death up to 30 days after randomisation.
- In addition, the endpoints using HF and CV hospitalisations will be repeated including urgent heart failure visits (see section 2.5.3)

Recurrent event analysis:

For the recurrent event analysis, descriptive statistics (total number of events, number of subjects with at least one event, number of events per subject, follow-up duration, rate per 100 subject-years) will be provided, and a negative binomial model will be used to estimate the rate ratio between treatment groups as described for the analysis of the primary endpoint (see section 4.6.1 for details). The analysis will be done for events occurring within 30 days of randomisation. For hospitalisations, the start date will be used. The analysis will be repeated to include all events happening during the 52 weeks after randomisation, i.e. up to the last known date or study day 375, whichever occurs first.

The joint frailty model will be fitted for the composite endpoints up to week 52 only.

Time to first event analysis:

For the time to first event analysis, the first occurrence of the relevant event will be used. The time to event in days will be defined as date of event – randomisation date + 1, with the date of event being the start date of hospitalisation (the earliest from the hospitalisation start date or emergency start date, when applicable) or date of death as appropriate. Prolonged index hospitalisations will have the start date for time to event analyses set to randomisation date.

For the analysis of events within 30 days after randomisation, only events starting within these 30 days will be taken into account. Subjects with no event at 30 days will be censored at 30 days or last known date, whichever comes first. For the analysis of events up to 52 weeks, the first incidence of the relevant event up to the last known date or study day 375, whichever occurs first, will be taken into account. Subjects with no event will be censored at last known date or study day 375, whichever occurs first. In addition, a sensitivity analysis will be performed looking at events up to last available value (see section 4.2.16).

The probability of subjects having an event will be displayed by treatment group in the form of cumulative probability curves estimated using the non-parametric Kaplan-Meier method. Point estimates and corresponding 2-sided 95% CIs using the Greenwood's variance estimator will be provided at each scheduled visit (i.e., Weeks 6, 12, 24, and 52). Percentiles (25th, 50th, and 75th) and corresponding 2-sided 95% CIs will also be provided; any of the percentiles not reached will be presented as N/A. Survival estimates at each time point where any patient had event or was censored will be also displayed.

The number of subjects with at least 1 event and the event hazard rate per 100 subject-years “at risk” (estimated as the number of subjects with at least 1 event divided by the subject-years at risk of event) will be displayed by treatment group. Subject-years at risk of event will be taken as the sum of the observation time from start of study drug until the first occurrence of the event concerned, or until censoring. The hazard ratio (relative to placebo), its 95% CI and the associated p-value will be provided using Cox proportional hazards regression.

SAS code for time to event Cox regression (code may be updated to fit the data)

Assume the response variable, time to first event, is TFE and the censored status variable is EVENT (0=censored observation; 1=event observation).

The option 'rl' in the model statement produces 95% CI for the hazard ratio.

```
PROC PHREG DATA=dataset ;  
    CLASS armcd(ref='Placebo') sex hf_aetio hf_duration country /param=glm;  
    MODEL tfe*event_0= armcd sex age hf_aetio hf_duration country  
        / risklimits type3;  
    contrast "IV FCM. vs Placebo" armcd 1 -1 /estimate=exp;  
    ods output parameterestimates=parmest;  
        ods output ContrastEstimate=ContrastEstimate;  
RUN;
```

NYHA functional class:

NYHA functional class is assessed at 6, 12, 24, and 52 weeks after randomisation as classes I, II, III, and IV. If a subject dies, then class V will be added for all remaining visits. If subject is hospitalised at any point during any post-baseline visit and this subject does not have any NYHA assessment for this visit (including imputed class V if subject dies), then class IV is imputed for such visit. For change from baseline categories, differences between actual classes will be calculated. The NYHA class will be analysed using a repeated measurement analysis of the ordered polytomous response, adjusted for treatment, time, and baseline NYHA class as well as minimization factors. The generalized estimating equations (GEE) method introduced by Liang and Zeger [10] will be used. This method uses marginal modelling of ordinal response, and it is appropriate when the regression parameters are the interest rather than the variance-covariance structure of the longitudinal data.

Similar sensitivity analyses will be performed without the imputation for subjects who die or are hospitalised.

A shift table presenting change in categories of NYHA from baseline to each visit and last available value will be provided (with imputation).

SAS code (code may be updated to fit the data)

scorechg_NYHA has values of 1, 2, 3, 4 for classes I, II, III and IV, respectively at 6, 12, 24, and 52 weeks. The model allows for missing values. Base corresponds to the baseline NYHA functional class.

```
proc genmod data=dataset rorder=internal ;  
    class armcd (ref==Placebo=) visit usubjid base sex hf_aetio hf_duration  
country;  
    model score_NYHA = armcd visit base sex age hf_aetio hf_duration country /  
dist=multinomial link=cumlogit;  
    repeated subject=usubjid/ type=IND;  
    estimate 'OR' armcd 1 -1 / exp;  
run;
```

Note: baseline included in the model. The odds ratio resulting from the ESTIMATE Statement Results indicates that the odds of IV FCM being in lower response categories is "X.XX" times the odds of Placebo being in lower response categories. Lower response categories are better for score_NYHA.

sources: <http://support.sas.com/resources/papers/proceedings16/11702-2016.pdf>;

Number of days lost due to HF hospitalisation or CV death:

The number of days lost due to HF hospitalisation within 30 days after randomisation and within 52 weeks after randomisation (up to the last known date or study day 375, whichever occurs first) will be calculated for each subject as the total number of days of HF hospitalisation (confirmed as being due to HF by CEC decision), excluding the index hospitalisation. Prolonged index hospitalisations will have the start date set to randomisation date and number of days lost will be computed from this day. The days lost due to CV death will be added to the number of days lost due to HF hospitalisation. This number of days will be summarised as a continuous variable by treatment group.

A negative binomial model similar to the one described in section 4.6.1 will be fitted on the number of days lost due to HF hospitalisation or CV death, with the log-transformed time on study of each subject in years as an offset.

Proportion of subjects with an event

An overall summary table presenting the number and proportion of subjects with an event (HF hospitalisations, CV hospitalisations, CV mortality; composite and individual categories) within 30 days of randomisation, within 52 weeks after randomisation (up to the last known date or study day 375, whichever occurs first) will also be presented. The following categories will be presented:

- Subjects with at least one HF hospitalisation (excluding and including urgent HF visits).
- Subjects with at least one CV hospitalisation.
- Subjects with CV death.
- Subjects with at least one HF hospitalisation (excluding and including urgent HF visits) or CV death.
- Subjects with at least one CV hospitalisation or CV death.

The p-value from Fisher's exact test will be used to compare the treatment groups. The proportions of subjects with an event will be compared using Fisher's exact test. In addition, the 95% confidence interval for the proportion using exact (Clopper-Pearson) estimates will be provided.

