- Change from baseline in the European quality of life – 5 dimensions questionnaire up to 52 weeks after randomisation.
- Days lost due to HF hospitalisations or CV death at 30 days after randomisation.

The analyses of secondary and other endpoints will be performed on the FAS and will use the CEC adjudicated events for hospitalisations and mortality-related outcomes.

For the recurrent event analysis, the same analysis as that described for the primary outcome will be performed.

For the time to first event analysis, the incidence of events will be documented by treatment group with the total number of events, the number of subjects with at least 1 event and the event hazard rate per 100 patient years “at risk” (estimated as the number of patients with at least 1 event divided by the patient years at risk of event). Patient years at risk of event will be taken as the sum of the observation time from start of study treatment until the first occurrence of the event concerned, or until censoring. The hazard ratio (relative to placebo), its 95% CI and the p-value test will be provided using Cox regression. The proportion of patients with an event (HF hospitalisations, CV hospitalisations, CV mortality; composite and individual categories) will also be reported.

The change in NYHA class will be analysed using a repeated measurement analysis of the ordered polytomous regression adjusted for treatment, time and the baseline NYHA value.

Complete details concerning the analyses of the other endpoints and the statistical tests to be performed will be detailed in the SAP – the latter will be finalised prior to unblinding of the trial database.

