4.2.11. Definition of First Study Day (SD1)

First study day (SD1) is defined as the date of first administration of IV FCM or placebo.

For efficacy assessments, study day will be computed from the randomisation into the study.

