4.2.14. Time on Study

Time on study for safety purposes is calculated for each subject from SD1 to the last known date:

$$\text{Time on study (days)} = (\text{Last Known Date} - \text{SD1}) + 1.$$

Time on study for efficacy purposes is calculated for each subject from randomisation date to the last known date:

$$\text{Time on study (days)} = (\text{Last Known Date} - \text{Randomisation Date}) + 1.$$

If last known date is outside of visit window for Week 52 visit (i.e. after study day 375), time on study will be 375 days for such subjects and only events up to this day will be considered.

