4.4. Subject Disposition

Subject disposition will be tabulated based on the screened population and will include the number screened subjects, randomised subjects, screened failures and subjects re-screened and randomised. If subject is re-screened, such subject will be calculated only once in the screened population. The reason for screen failure will be provided. All screen failure reasons including reasons if subject was re-screened, will be summarized.

In addition, the number of subjects randomised, treated, started treatment after and not on the randomisation date, randomised not-treated, who received a different treatment that they were randomised to, who discontinued treatment, discontinued study, discontinued treatment but completed study along with the reason for treatment discontinuation and the reason for study discontinuation will be provided based on All Randomised Set. The number of subjects in each population with reason for exclusion will be provided based on All Randomised population.

A by-subject listing of study withdrawal/completion information, including the reason for premature study withdrawal, if applicable, will be presented.

Protocol deviations will be listed.

In addition, Kaplan-Meier (KM) curves for time to discontinuation, censoring at last visit (see section 4.2.13), will be plotted by treatment group for the FAS.

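### The descriptive first-event rate per 100 subject-years counts time at risk from first dose, while the time to the same events runs from randomisation

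*SAP*

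**What the plan says.** SAP 4.6.2, under the time to first event analysis, reports for each arm the number of subjects with an event divided by the subject-years at risk. The denominator is defined thus: "Subject-years at risk of event will be taken as the sum of the observation time from start of study drug", up to the first event or censoring. Protocol 12.7.2 has the same rule in its own words: "Patient years at risk of event will be taken as the sum of the observation time from start of study treatment".

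Earlier in the same SAP section the event time itself is defined differently: "The time to event in days will be defined as date of event – randomisation date + 1". A special rule follows: "Prolonged index hospitalisations will have the start date for time to event analyses set to randomisation date".

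The general definitions side with randomisation. SAP 4.2.11: "For efficacy assessments, study day will be computed from the randomisation into the study". SAP 4.2.14: "Time on study for efficacy purposes is calculated for each subject from randomisation date to the last known date"; the version that starts at first dose is kept there for safety. The recurrent-event rates use the efficacy version.

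The SAP expects the two dates to differ for some subjects. SAP 4.4 tabulates those who "started treatment after and not on the randomisation date", SAP 4.8.2 plans a listing of adverse events that fall in the gap, and SAP 7.1 lists late starters (listing 16.2.1.3).

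**The concern.** A rate needs its events and its person-time on one clock. Here the events are dated from randomisation, but the person-time begins at first dose. The late starters remain in the full analysis set, which requires that dosing was started at some point and not that it was started on the randomisation day (SAP 3.1). For them the time at risk is short by the lag.

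The re-dating of prolonged index hospitalisations makes this more than a loss of a day or two. Such an event sits on the randomisation date. If the first dose came later, the event precedes the start of the subject's own time at risk, and the SAP has no rule for that case. The programmer would have to drop the subject, truncate at zero, or add a negative number to the total.

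At stake is a reported figure, not a test. The rate is printed beside a hazard ratio and a Kaplan-Meier curve with another origin. Across the efficacy tables, a rate per 100 subject-years would mean one thing for recurrent events and another for first events.

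**Working it through.** The documents give no figure for this rate, so there is none to reproduce. The check has two parts.

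**One subject.** Take a prolonged index hospitalisation that counts as an event, with event date = randomisation date and first dose L days later.

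- Randomisation clock (SAP 4.6.2): event date − randomisation date + 1 = 1 day at any L.
- Dose clock with the +1 convention: event date − first-dose date + 1 = 1 − L.
- Dose clock without +1: −L. The denominator sentence does not say which convention applies.

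| Lag L (days) | Randomisation clock | Dose clock, +1 | Dose clock, no +1 |
|---|---|---|---|
| 0 | 1 | 1 | 0 |
| 1 | 1 | 0 | -1 |
| 2 | 1 | -1 | -2 |
| 3 | 1 | -2 | -3 |

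Zero or negative time thus follows from the written rules.

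**One arm.** Inputs from the documents: 35% of subjects with a first event (SAP 4.1), taken here as the risk by day 364. Assumptions: exponential event times, and a share f of subjects dosed L days late.

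- Daily hazard: λ = −ln(0.65)/364 = 0.0011835, or 0.0011835 × 36,525 = 43.23 per 100 subject-years.
- Mean time at risk to horizon H: m = (1 − e^(−λH))/λ. For H = 364, m = 295.74 days; for H = 30, m = 29.47 days.
- On the dose clock each late starter loses L days, so the rate is multiplied by m/(m − fL). The number of subjects cancels.

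| f | L (days) | 52 weeks: factor, rate | 30 days: factor, rate |
|---|---|---|---|
| 5% | 1 | 1.0002, 43.23 | 1.0017, 43.30 |
| 10% | 1 | 1.0003, 43.24 | 1.0034, 43.37 |
| 10% | 3 | 1.0010, 43.27 | 1.0103, 43.67 |
| 100% | 1 | 1.0034, 43.37 | 1.0351, 44.74 |
| 100% | 3 | 1.0102, 43.67 | 1.1133, 48.12 |

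For example, with f = 10% and L = 3 at 30 days: 29.47/(29.47 − 0.3) = 1.0103. Cutting at study day 375 instead of 364 gives the same 52-week factors to within 0.0002. The last two rows are extremes, shown only to bound the effect.

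**The case against.** The case for leaving the rule alone has four parts.

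1. Most passages require the first dose on the day of randomisation (synopsis Procedures row; protocol 4.1.2 and 9.2.3.12; Table 2, footnote 10), and SAP Appendix I codes dosing away from randomisation as a major deviation (PDIMP09). For subjects dosed that way the clocks agree. This stands as a limit on size. It does not remove the gap: the synopsis Treatment row only recommends same-day dosing, and the SAP plans for exceptions.

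2. The schedule starts the check for endpoint events at the start of study treatment (footnote 14), which looks like a reason for a dose origin. That footnote governs data collection. The analysis rules still date events from randomisation and move prolonged index stays back to it.

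3. Full analysis set members must have lived to be dosed, so for the mortality endpoints the gap is free of events by construction. That is true, but it applies equally to the Kaplan-Meier and Cox clock the SAP has already chosen. It does not justify a second clock for one rate in the same analysis.

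4. A reader might infer that any event between randomisation and first dose yields negative time. The documents do not support so broad a reading. The subject is still in hospital for the index stay, so a new admission in the gap is implausible, and a subject who dies undosed is outside the full analysis set. The route is chiefly the re-dated prolonged index hospitalisation, so the problem concerns endpoints that include hospitalisation. For the mortality endpoints only the small understatement remains.

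Nor is this the only efficacy definition tied to first dose: baseline is as well (SAP 4.2.12).

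**Conclusion.** The inconsistency is real and the written rules can produce impossible person-time, but its reach is narrow. Only the descriptive rate per 100 subject-years for first events is affected. Under the assumption that 5-10% of subjects are dosed 1-3 days late, the rate is inflated by about 0.1% or less at 52 weeks and by roughly 0.2% to 1.0% at 30 days. Share and lag are both assumptions, since the documents give neither.

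A reader might go on to doubt the hazard ratios, the p-values or the primary result. The documents do not support that: the Kaplan-Meier curves, the Cox models, the primary negative binomial model and the tests entering the Hochberg procedure all run from randomisation. This is a minor correction, worth making before programming.

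**What to change.** In SAP 4.6.2, define subject-years at risk as the sum over subjects of (event or censoring date − randomisation date + 1), divided by 365.25, with the censoring rules already given there for 30 days and 52 weeks. This is the sum of the time-to-first-event variable, so the rate, the curve and the hazard ratio share one clock, and a prolonged index hospitalisation contributes 1 day at any lag.

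Protocol 12.7.2 has its own dose-based wording, so the change is a departure from the protocol. Record it in SAP section 5, which at present lists only the handling of age. That one recorded departure is the cost. Rewording the protocol itself would need an amendment with regulatory and ethics review (protocol 16.2). No test, estimate or sample size changes.

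Separately, the protocol passages on first-dose timing must be reconciled: the synopsis Treatment row recommends the randomisation day, while the synopsis Procedures row and sections 4.1.2 and 9.2.3.12 make it mandatory.

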4.2.9. Visit Windows

For summaries by timepoint, the time windows given in Table 3 will be applied to allocate measurements to analysis visit. This will be done for laboratory parameters, vital signs, ECG, NYHA Classification, KCCQ-12, and EQ-5D.

In general, in case multiple measurements are collected in the same window, the value closest to the target day as specified in Table 3 will be used for analysis. If there are 2 values with the same time before and after the target day, the later value will be used for analysis. If there are 2 continuous values on the same date then the average of the values will be used. For categorical variables, if there are more than 1 value on the same date then the worst case will be chosen (e.g. for EQ-5D).

Table 3 Analysis Assessment Windows

Parameter	Visit Label	Analysis Assessment Window (Efficacy/Safety)
Laboratory parameters, Vital signs, ECG, NYHA Classification	Baseline	≤1 day
	Week 6	Day 43 [2; 64] days
	Week 12	Day 85 [65; 107] days
	Week 24	Day 169 [108; 253] days
	Week 52	Day 365 [254; 408] days
EQ-5D	Baseline	≤1 day
	Week 6	Day 43 [2; 85] days
	Week 24	Day 169 [86; 253] days
	Week 52	Day 365 [254; 408] days
KCCQ-12	Screening	N/A
	Baseline	≤1 day
	Week 2	Day 14 [2; 20] days
	Week 4	Day 28 [21; 34] days
	Week 6	Day 43 [35; 64] days
	Week 12	Day 85 [65; 107] days
	Week 24	Day 169 [108; 211] days
	Week 36	Day 253 [212; 295] days
	Week 52	Day 365 [296; 408] days

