4.2.13. End of Study (Last Visit)

End of study is defined as the date of the Week 52 visit for subjects completing the study, or the date of the early study termination visit for other subjects.

In cases where the subject dies, if the last visit is reported after death then death date will be used as last day in study.

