4.2.16. Last Available Value

The last available value is defined as the last available value across visits, including unscheduled measurements.

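### Days lost: days after CV death are counted, but the model offset runs to an undefined last known date that most naturally stops at death, so a few early deaths can dominate the rate ratio

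*SAP*

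**What the plan says.** Days lost up to 52 weeks is one of five secondary endpoints, tested by Hochberg's procedure once the primary is rejected (SAP 2.5.2 and 4.6.2).

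- **Count.** HF-hospital days are taken "up to the last known date or study day 375, whichever occurs first". Then: "The days lost due to CV death will be added to the number of days lost due to HF hospitalisation". No first or last day is given for the CV-death part.
- **Model.** A negative binomial model like that of SAP 4.6.1 is fitted to the days "lost due to HF hospitalisation or CV death, with the log-transformed time on study of each subject in years as an offset".
- **Offset.** SAP 4.2.14: "Time on study for efficacy purposes is calculated for each subject from randomisation date to the last known date". If that date falls after study day 375, "time on study will be 375 days for such subjects and only events up to this day will be considered".
- **Nearby definitions.** SAP 4.2.13 covers End of Study: "if the last visit is reported after death then death date will be used as last day in study". SAP 4.2.16 covers another term: "The last available value is defined as the last available value across visits, including unscheduled measurements". Neither defines last known date.

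**The concern.** A rate model needs the count and the exposure to cover the same period. Here the count can include days after death, while the offset may end at death. A subject who dies early then combines a very large count with a very small exposure, and the estimated ratio depends on which arm has the earliest one or two deaths. The model's standard error need not reflect this. Hochberg's procedure controls error only if the p-values it receives are valid.

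If lost days are also cut at death, the problem is different: CV death adds nothing, and the endpoint does not measure what its name says.

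**Working it through.** **Plan's own figure.** The documents give no operating figure for this endpoint, only the primary sample size. With n = (z₀.₉₇₅√V₀ + z₀.₈₀√V₁)² / (ln RR)², r₀ = 0.7, RR = 0.75, K = 1 and t = 11/12 year:

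- V₀ = (1/t)(2/r₀) + 2K = 5.117
- V₁ = (1/t)(1/r₀ + 1/r₁) + 2K = 5.636
- n = (1.960 × 2.262 + 0.842 × 2.374)² / 0.0828 ≈ 500 per arm, and 500/0.91 ≈ 550

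This matches the plan.

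**Which reading is natural.** The same time on study is the exposure for the primary endpoint (SAP 4.6.1), where person-time has to stop at death, and the End of Study rule also points to the death date. The cut-off wording in SAP 4.6.2 is attached to HF-hospital days; the CV-death days are added in a later sentence. So exposure ending at death, with lost days running on, is the most natural reading, although the SAP does not state it.

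**One subject's contribution** (window to day 375):

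- Offset ending at death, death on day 10: (375 − 10)/(10/365.25) ≈ 13,300 days per year.
- Offset ending at death, death on day 200: (375 − 200)/(200/365.25) ≈ 320 days per year.
- Full-window offset: 365/(375/365.25) ≈ 356 and 175/(375/365.25) ≈ 170 days per year.

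The contrast between the two deaths is about 42-fold in the first case and about 2-fold in the second.

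**One simulated trial.** Moving a single FCM death from day 200 to day 30, 7 and 1 changed the rate ratio from 1.30 (p = 0.19) to 1.45 (p = 0.07), 2.03 (p = 0.0007) and 6.3. With the full-window offset it stayed at 1.16 to 1.17 (p = 0.37 to 0.42).

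**Null simulations**, 550 per arm.

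- *From the SAP:* 12% CV death; 2 × (35 − 6) = 58 HF stays per 100 subject-years.
- *Set-up A:* no covariates, window to day 375, K = 1, 1,600 trials per row. Assumed: mean stay 9 days, 3% non-CV death, 4% withdrawal.
- *Set-up B:* the SAP's covariates with country or the region fallback, window to day 365, 9% loss, 1,000 trials per row. An HF stay occurs in 50% of CV deaths and (29 − 6)/88 = 26.1% of the others. Assumed: mean stay 10 days.
- *Death timing is assumed in both.*

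Rejection at nominal 5%:

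| CV-death timing | A | B region / country | Matched offset, A; B |
|---|---|---|---|
| Uniform from day 1 | 52% | 31% / 22% | 3%; 1% |
| Front-loaded | 4–46% | 33% / 24% | 1–2%; 0.5–1.3% |
| None in about the first week | 27% | 17% / 15% | 2%; 1–2% |
| None in about the first month | 13% | 6% / 6% | 3%; 1% |
| Uniform from day 60 / 90 / 120 | 8 / 6 / 5% | – | 2–3% |

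Monte Carlo error is up to about 3 points. Across all runs the matched offset gave about 0% to 5%.

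The range is not a bound: set-up A with 8% CV death and uniform timing gave 58%. Covariate coding matters too: without covariates, inputs like those of set-up B gave 43% to 46% for uniform deaths. At the 1% level, Hochberg's smallest critical value, set-up A ran from about 1% to 40% over the table's timings.

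**Why it rejects.** In set-up A with uniform deaths, the log rate ratio had SD 0.69 across trials against a model standard error of 0.23. With the matched offset these were 0.16 and 0.18. Under the most extreme front-loading they were 0.27 and 0.28, which is why that case is not inflated.

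**If lost days are also cut at death,** set-up B rejected in 0.6% to 2.3%. There is no inflation, but CV death adds nothing.

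**The case against.** **The SAP does not compel the mismatch.** Last known date is undefined and the model is only described as similar to the primary one, so full-window follow-up for deaths in the offset is a third possible reading. This stands. The point is conditional on exposure stopping at death, and the gap has to be closed under any reading.

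**The percentages depend on assumptions.** This also stands. A reader might take a third or a half as the test's error rate, or as a ceiling. The documents give neither death timing nor length of stay, so no such figure follows from them.

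**The gate protects.** Under a complete null it limits false secondary claims to about 5%. It does not when the primary effect is real. A reader might then want a formal false-claim rate. In one constructed case (FCM stays 30% fewer but proportionally longer, equal CV death), Hochberg claimed days lost in 11% of gate-passed trials with uniform deaths and in 3% with no CV death before day 31. Nothing in the documents suggests such offsetting stays, and the case also assumes 0.15 non-HF CV hospitalisations per year. It shows that the gate can fail to protect, not by how much.

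**The endpoint has little power anyway.** Largely true. With uniform deaths and 10-day stays, mean days lost is about 0.12 × 182.5 = 21.9 from death plus 0.58 × 10 = 5.8 from HF stays. A 30% cut in stays removes about 1.7 of 27.7 days. Low power is therefore not only the offset's doing.

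**The day-375 limit might look like a second bias.** The endpoint is named as 52 weeks and the Week 52 target is "Day 365 [254; 408] days". If CV-death days ran to day 375, each death would gain 10 days, or 0.12 × 10 = 1.2 days per subject. The SAP does not say that they do, and the excess is equal between arms when deaths are equal. This is a separate and minor point.

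**Conclusion.** The point holds and should be fixed before unblinding. The SAP adds CV-death days without a start or end and offsets them by a time on study whose end date it does not define. On the natural reading the count runs past the exposure, and a few early deaths can dominate the rate ratio.

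The mechanism is well supported, because the same data with a matched offset show no inflation. The size is uncertain: about 4% to 52% rejection at nominal 5% for the single ungated test, highest when deaths can occur in the first days, and about 6% to 13% at the planned 12% CV death with none in the first month. All of this rests on assumed death timing, length of stay and covariate coding.

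The consequence is limited to one gated secondary endpoint and its repeats in other sets and subgroups. The primary endpoint is unaffected, and days lost are also summarised by arm.

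**What to change.** In the SAP, before unblinding:

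1. Define last known date as the death date for subjects who die.
2. Count days lost to CV death from death to one fixed window end common to all subjects, and to day 30 for the 30-day version.
3. Use that same window as the offset for subjects with CV death, and time on study capped at that window for everyone else.
4. Apply the rule to the per-protocol and subgroup versions, and to the COVID-19 version with the window ending at the earlier of the fixed day and the country index date.

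Separately, state whether the window ends at the Week 52 target (day 365) or at day 375.

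The cost is SAP wording and one endpoint reprogrammed, with no new data. The drawback is that the aligned model-based test is conservative, with about 2.6% power under the plan's own alternative in set-up B; the SAP should say so. A permutation test of mean fixed-window days lost is an option. A Welch test used as a stand-in for it was close to nominal under the null (4.1% to 5.9%) but had only 6.6% power, so it improves calibration more than sensitivity.
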